## **7.5. Exploratory Endpoint Analysis**

None planned at this time.

## **7.6. Missing Data**

We will test the pattern of missing values using Little's MCAR test, and, assuming that the data are missing at random, we will employ statistical procedures that are based on maximum likelihood estimates, which will allow the inclusion of all subjects without imputation of missing values. The maximum likelihood approach estimates the parameter values that would maximize the probability of observing the data collected. In the event of missing variables, the likelihood for a given individual is the probability of observing the non-missing variables. Thus, the maximum likelihood approach allows the use of data from participants for the time period for which data is available, but not for time periods for which the data is missing. This procedure uses information from earlier time periods to estimate the effects of later time periods, while also accounting for the uncertainty of the projection in the computation of standard errors and test statistics. While maximum likelihood estimation is considered superior to imputation methods for the treatment of missing data in clinical trials, additional analyses will be conducted using several imputation methods to test the sensitivity of these results. Imputations methods will include, but not be limited to, last observation carried forward and multiple imputation with the Markov Chain Monte Carlo (MCMC) method carried out in PROC MI in SAS.

In the case of non-random missing data, we will conduct sensitivity analyses using

multiple imputation with the Markov Chain Monte Carlo (MCMC) method carried out in PROC MI in SAS. If missing data is associated with experimental condition, we will conduct multiple imputation for each experimental condition. At least 10 imputed data sets will be generated, with the experimental-condition effect being assessed in each imputed data set. A final single assessment of experimental condition differences will be obtained from combining the results across the imputed datasets using PROC MIANALYZE in SAS. The results of these analyses will be compared to the primary analysis to evaluate the robustness of our conclusions.

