Any SAE will be brought to the attention of the site PIs as soon as possible and not longer than 24 hours. Any AE or SAE that is both unexpected and related to study participation will be reported to the IRB within 7 days of the event. The IRB will make a determination as to whether additional reporting requirements are needed. IRB actions will be reported to the funding agency by the PIs no less than annually and more frequently as recommended by the local IRB. Any SAEs will be summarized in the yearly Progress Reports to the funding agency, including a review of frequency and severity. All SAEs will be followed through ongoing consultation with the physician caring for the patient until they resolve, result in death, or stabilize and are not expected to improve. The study staff will be in close contact with participants and health care providers throughout the study to monitor for potential unanticipated problems. Any unanticipated problems will be discussed at the weekly research staff meetings and reported as required to the local IRB.

Withdrawal or Monitoring of Participants

For the participant's protection, participants will be withdrawn immediately from the study if any of the following occur:

- 1) Pregnancy complication: Typically includes miscarriage, stillbirth, or preterm delivery.
- 2) Cardiovascular disease (CVD) event: Typically includes MI (heart attack), PTCA (angioplasty/stenting), bypass surgery, stroke, peripheral vascular disease (arterial blockages in arms or legs leading to procedure or surgery). Less common CVD problems would be new cardiac arrhythmias (e.g., new atrial fibrillation) or new valvular disease (e.g., mitral or aortic regurgitation).
- 3) Deep vein thrombosis (DVT)/pulmonary embolism (PE): I.e., blood clots in the venous system.
- 4) Suicide attempt: A participant will be withdrawn if she attempts suicide at any time during participation in the study.
- 5) Psychiatric hospitalization: A participant will be withdrawn if she is hospitalized for psychiatric reasons at any time during participation in the study.

- 6) Expired breath CO increase: A participant will be withdrawn from the study if the average of two consecutive CO readings during the same visit is more than double their Baseline exhaled CO measurement, or greater than 50 ppm at any given time.

The following will be monitored and can lead to the participant being withdrawn by the PI or Licensed Medical Professional:

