### **5.2. Per-Protocol Population**

A separate per-protocol population will also be used for this study, with the results from these analyses compared to those of the full analysis population in order to examine whether missing data affects the outcomes of interest. Participants who complete the 12-week protocol will represent the per-protocol population.

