## **7.3. Primary Endpoint Analysis**

### **7.3.1. Primary Analysis**

The primary endpoint is CPD during Week 12, compared to the CPD at baseline. While the primary outcome is the mean total CPD, consisting of both study and non-study cigarettes, the analyses will be repeated examining only the CPD contributed by study cigarettes. CPD will be computed as the mean CPD calculated on a weekly basis. Data analysis will use repeated measures analysis of variance, with two conditions and two time points (baseline and Week 12). In addition, the analysis model will include a random effect for site, a random

participant effect and random error (within-subject error). Variance parameters will be estimated using restricted maximum likelihood method with the Satterthwaite approximation.

Because CPD will be measured weekly, additional analyses will be performed including data collected at all time points. The analysis will be conducted in a manner similar to that described above, with the exception that there will be 13 time points: baseline and Weeks 1 through 12. For these analyses, the variance-covariance structure will be specified as first-order autoregressive.

Additional outcomes include the CPT, breath CO level, urinary cotinine concentration, and nicotine dependence and withdrawal scores. These will be examined in a manner similar to that described above for CPD. Natural log transformations will be performed as needed so that ANOVA model assumptions of normality and equal variances hold. Geometric means in original units will be calculated as well. Note that not all outcomes are assessed at weekly in-person visits. The time points at which each outcome is assessed is described in Section 6.

Finally, several assessments will be made at baseline as well as at the abstinence visit, which occurs the day following the Week 12 assessment. At this visit, measures of craving and withdrawal will be completed. The analysis will be similar to that described above for the CPD comparing baseline CPD to that reported at the end of the trial. The analysis will deviate from that described only in the timing of the tasks, with the time points consisting of the baseline and the abstinence visits, rather than the baseline and Week 12 visits reported above.

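### The only method SAP 7.6 names for non-random missing data, unshifted multiple imputation, still assumes missing at random, so it cannot show robustness to data missing not at random

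*SAP*

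**What the plan says.** SAP 7.6 opens with Little's MCAR test and then sets the primary approach: "assuming that the data are missing at random, we will employ statistical procedures that are based on maximum likelihood estimates". It adds sensitivity analyses by imputation: "Imputations methods will include, but not be limited to, last observation carried forward and multiple imputation with the Markov Chain Monte Carlo (MCMC) method".

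A separate paragraph deals with the harder case: "In the case of non-random missing data, we will conduct sensitivity analyses using" MCMC multiple imputation in PROC MI. It continues: "If missing data is associated with experimental condition, we will conduct multiple imputation for each experimental condition". At least 10 imputed data sets are pooled in PROC MIANALYZE, and the paragraph ends: "The results of these analyses will be compared to the primary analysis to evaluate the robustness of our conclusions".

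Three other places bear on the point:
- **SAP 7.3.1** fits the primary CPD model to two time points, baseline and Week 12. It also plans an additional CPD analysis with 13 time points and a first-order autoregressive structure.
- **SAP 5.2** compares 12-week completers with the full analysis population "in order to examine whether missing data affects the outcomes of interest".
- **SAP 5.1** analyses women by assigned condition whatever their compliance.

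The Study 2 statistical section of the protocol names no sensitivity method for missing data.

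**The concern.** A sensitivity analysis tests an assumption only if it relaxes that assumption. Likelihood under MAR and multiple imputation without a shift both predict a missing Week 12 value from women with similar observed data who stayed. Running the imputation separately in each condition lets that prediction differ by arm, but it is still a MAR prediction. The two methods should agree closely whether or not MAR holds, and SAP 7.6 would count that agreement as evidence of robustness.

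The term non-random is also open to two readings. If it means not missing completely at random, imputation by condition is a reasonable response, but then no analysis for data missing not at random is named at all. Little's test cannot separate MAR from missing not at random, so it cannot decide when such an analysis is needed.

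At stake is how the Week 12 CPD result is reported. If VLNC women who leave go back to smoking as before, both planned methods give a larger effect than the one among all women randomised, and nothing in the named plan would show by how much.

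**Working it through.** **1. The plan's own figures.** 90 completers / (1 − 0.15) = 105.9, so 106 randomised (53 per arm); with 5 pilot participants this is 111, as stated. The stated 80% power cannot be reproduced directly because no SD is given. A two-sided t-test with 45 per arm, a difference of 5 CPD and 80% power implies an SD of 8.37 for a single CPD value.

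**2. What each named analysis assumes.**

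| Analysis | Assumption about missing Week 12 CPD | Departure varied? |
|---|---|---|
| Two-point likelihood (7.3.1) | MAR given baseline | No |
| 13-point AR(1) likelihood (7.3.1) | MAR given observed weekly CPD | No |
| MCMC imputation, overall or by condition (7.6) | MAR given the imputation model | No |
| LOCF (7.6) | Equals the last observed value | No, one fixed assumption |
| Completers (5.2) | Changes the set analysed | No |

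**3. Do the two MAR methods move together?** An illustrative simulation used assumed values: 53 per arm, SD 8.4, correlation 0.6, an effect of −5 CPD under MAR, 10 imputations and 1,500 runs. Missing VLNC women smoke delta CPD more than MAR predicts.

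| Missing | Delta | Full data | MAR likelihood | Unshifted imputation by arm | Shifted imputation |
|---|---|---|---|---|---|
| 15% | 3 | −4.56 | −5.02 | −5.02 | −4.57 |
| 15% | 5 | −4.21 | −4.98 | −4.99 | −4.24 |
| 30% | 3 | −4.13 | −5.00 | −5.01 | −4.10 |
| 30% | 5 | −3.51 | −4.99 | −4.99 | −3.50 |

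Unshifted imputation matches MAR likelihood to within 0.01 CPD throughout. Only the shifted version follows the full-data value.

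**4. Size for this trial.** Assumptions: usual-brand women stay at baseline on average with 15% dropout; VLNC women without Week 12 CPD return to their own baseline; the correlation r between baseline and Week 12 is 0.3, 0.5 or 0.7 (not in the documents). With VLNC dropout f:
- Effect among all randomised = 5 × (1 − f); overstatement = 5 × f.
- SD of change = 8.37 × √(2(1 − r)).
- SE = SD of change × √(1/nV + 1/45.05), where nV = 53 × (1 − f).

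| f | nV | Effect | Overstatement | SE (r = 0.3 / 0.5 / 0.7) | z = effect / SE |
|---|---|---|---|---|---|
| 15% (planned) | 45.05 | 4.25 | 0.75 | 2.087 / 1.764 / 1.366 | 2.04 / 2.41 / 3.11 |
| 25% (assumed) | 39.75 | 3.75 | 1.25 | 2.155 / 1.821 / 1.411 | 1.74 / 2.06 / 2.66 |
| 35% (assumed) | 34.45 | 3.25 | 1.75 | 2.241 / 1.894 / 1.467 | 1.45 / 1.72 / 2.21 |

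The critical value is about 1.99. At 15% the tipping shift, (5 − 1.99 × SE) / 0.15, is 5.7, 10.0 and 15.2 CPD for the three r values, against 5 for full return to baseline.

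**5. Which r fits the stated power?** At r = 0.5, √(2(1 − r)) = 1, so the change contrast has SD 8.37 and the stated 80% power. At r = 0.3 the change SD is 9.90 and power at 45 per arm is about 66%. If the stated power refers to the planned baseline-to-Week 12 contrast, r = 0.5 is the relevant column. There z crosses the critical value near 27% VLNC dropout: nV = 38.69, SE = 8.37 × √(1/38.69 + 1/45.05) = 1.835, effect 3.65, z = 1.99.

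**The case against.** **Planned analyses already help.** The 13-time-point model uses all observed weekly CPD, so dropout that depends on recorded CPD is addressed by a named analysis. LOCF does not rest on MAR, and the list of methods is open-ended. This stands as far as it goes. But the 13-point model still assumes MAR given what was observed, LOCF is a single fixed assumption, and an open list commits to nothing.

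**The CO withdrawal rule.** A reader might infer that the protocol builds in data missing not at random, because Withdrawal or Monitoring of Participants removes a woman when the average of "two consecutive CO readings during the same visit is more than double their Baseline exhaled CO measurement". The documents do not support that reading. The trigger is a recorded measurement, so this loss can be MAR given CO. The rule argues for CO as a predictor in the imputation model, not for a shift.

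**Other reasons for loss.** The same section withdraws women for miscarriage, stillbirth or preterm delivery, and entry is allowed up to 25 weeks of gestation before a 12-week exposure period. Some Week 12 values may be missing because of delivery or complications, where return to baseline smoking is less obvious. This stands, and it is a reason to report a range of shifts and not one scenario alone.

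**The estimand.** Treating return to baseline as the true effect presumes a treatment-policy reading. SAP 5.1 leans that way, but the SAP does not say how smoking after withdrawal is to be handled. The word overstated holds only on that reading.

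**The result is fragile.** A reader might also infer that the primary conclusion would fall. At the planned attrition, expected significance survives for every r tried. Losing it needs dropout beyond the plan.

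**Conclusion.** The point holds as a minor improvement. SAP 7.6 offers agreement between two MAR analyses as evidence of robustness for non-random missingness, and no named analysis varies the departure from MAR. Neither the LOCF analysis nor the completer comparison fills that gap.

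On a treatment-policy reading, with VLNC women lacking Week 12 CPD assumed to return to their own baseline, the overstatement is about 0.75 of 5 CPD at 15% attrition, and significance is expected to survive. At r = 0.5, the value consistent with 80% power for the change contrast, expected z is 2.06 at 25% VLNC dropout and 1.72 at 35%. Those dropout rates, the SD and r are assumptions or back-calculations. They illustrate scale and do not predict this trial's result.

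**What to change.** Amend SAP 7.6 for Week 12 total CPD, to apply whatever Little's test shows:

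1. Pre-specify delta-adjusted multiple imputation by condition. Use a reduced set of observed CPD and breath CO values as predictors, so that the model is stable at about 53 women per arm.
2. Shift imputed VLNC values in 1-CPD steps, up to and beyond return to baseline. Pool in PROC MIANALYZE and report the tipping point.
3. Name return to own baseline as one scenario, and note that it is less obvious for loss after delivery or a pregnancy complication.
4. Label the unshifted MCMC imputation as a check under MAR.
5. In SAP 5.2, do not present the completer comparison as a test of the missing-data assumption.

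The cost is SAP wording and a little more programming, including the choice of a compact imputation model. The sensitivity result may be less favourable. No new data are needed, and the primary estimate and test do not change.

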#### **4.2. Sample Size**

Sample size was determined using power analysis for hypothesis tests related to the Primary Aim of Study 2, specifically to detect a significant difference between the VLNC condition and the UB condition in the primary endpoint, cigarettes per day (CPD), at the end of the trial. Effect size estimates were based on our previous studies of normal nicotine cigarettes (NNC) and VLNC use in disadvantaged women of childbearing age and estimates of CPD in our completed study on smoking topography in pregnant women and women of childbearing age. In that study, pregnant women smoked an average of 12.1 CPD, while preliminary data from our trial of women of childbearing age suggest a decrease of 5 CPD in women smoking VLNC compared to those smoking NNC. A sample size of 45 completers per condition will provide 80% power to detect statistically significant differences in smoking rate, with significance level alpha = 0.05.

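### SAP 7.6 makes imputation by condition depend on whether missingness differs by arm, which is the wrong trigger, and nothing else in the SAP keeps condition in the imputation model

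*SAP*

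**What the plan says.** SAP 7.6 (Missing Data) handles missing outcomes in three steps.

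- **Primary.** Maximum likelihood under missing at random (MAR), "which will allow the inclusion of all subjects without imputation of missing values".
- **Sensitivity, MAR.** Imputation methods that include "last observation carried forward and multiple imputation with the Markov Chain Monte Carlo (MCMC) method carried out in PROC MI in SAS". This paragraph does not mention condition.
- **Sensitivity, non-random missingness.** MCMC multiple imputation again, with this rule: "If missing data is associated with experimental condition, we will conduct multiple imputation for each experimental condition". It adds: "At least 10 imputed data sets will be generated, with the experimental-condition effect being assessed in each imputed data set". The purpose is then stated: "The results of these analyses will be compared to the primary analysis to evaluate the robustness of our conclusions".

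The conditional sentence is the only statement on how condition enters the imputation. Section 7.6 does not say what is done when missingness is unrelated to condition, how that relation is to be judged, or which variables go into the imputation model. The Study 2 statistical section of the protocol does not describe multiple imputation.

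**The concern.** The analysis model contains condition, time and their interaction. An imputation model that feeds it should be at least as rich. If condition is left out, a woman missing Week 12 receives a value from a relation averaged over both arms, so the imputed women carry little of the arm difference. Two ingredients cause this: a treatment effect and some missing outcomes. Unequal missingness is not one of them. The trial is designed around an effect and plans for attrition, so both ingredients are expected even if dropout is identical in the arms.

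At stake is how the sensitivity analysis would be read. If condition were omitted, the imputed and primary results would diverge even under completely random missingness, and a sound primary result could look fragile because of the imputation model alone.

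**Working it through.** **Inputs from the documents**

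- Effect: "preliminary data from our trial of women of childbearing age suggest a decrease of 5 CPD in women smoking VLNC" (SAP 4.2).
- Mean level: "In that study, pregnant women smoked an average of 12.1 CPD" (SAP 4.2).
- 45 completers per condition, 80% power, alpha 0.05 (SAP 4.2); two-sided testing is assumed.
- 15% attrition and five pilot participants (SAP 4.1).
- 106 randomized, equal allocation (protocol, Study 2 Randomization), so 53 per arm.

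**The plan's own figures.** 90 / (1 − 0.15) = 105.9, rounded up to 106; 106 + 5 = 111, which matches. No SD is given. Solving the power statement for it: SD = 5 × √(45/2) / (1.960 + 0.842) = 8.47 (normal) or 8.37 (t). An SD of 8.4 is used below; it gives power of 0.806.

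**Expected shrinkage.** Let m be the fraction missing and k the share of the arm difference that reaches the imputed values through the predictors. With condition omitted,

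estimate ≈ effect × [1 − m(1 − k)].

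Baseline CPD is balanced by randomization, so imputing from baseline alone gives k ≈ 0: 5 × (1 − 0.15) = 4.25 CPD, a 15% loss. Post-baseline CPD that already shows the effect raises k and reduces the loss. If women leave before contributing such data, k falls back toward 0.

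**Simulation.** 53 per arm, true difference −5 CPD, missingness completely at random and equal in both arms, 10 imputations by Bayesian normal regression, Rubin's rules, 1,500 trials per scenario. Assumed: SD 8.4, baseline to Week 12 correlation 0.3 to 0.7, missingness 10% to 30%.

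| Imputation from baseline only | Mean difference, 15% missing | Trials significant |
|---|---|---|
| Joint, condition omitted | −4.19 to −4.29 | about 68% |
| Joint, condition included | −4.93 to −5.07 | 79.9% to 80.9% |
| Separately by condition | −4.94 to −5.06 | 80.1% to 80.5% |

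With condition omitted, the estimate is −4.42 to −4.50 at 10% missing, −3.72 to −3.76 at 25%, and −3.44 to −3.49 at 30%. At 30%, 41% to 46% of trials are significant, against 69% to 77% when imputing by condition.

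**With post-baseline data.** Adding one observed intermediate week that carries the effect gives −4.66 to −4.93 at 15% missing with condition omitted. The loss is (5 − 4.66)/5 = 6.8% down to (5 − 4.93)/5 = 1.4%. Less favorable dropout timing and correlations take it to about 13%, or 5 × 0.87 = 4.35 CPD. A joint model with condition included shows no shrinkage in any scenario (−4.89 to −5.09).

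**Reliability of the trigger.** The SAP names no test or threshold. If a two-sided 5% test were used, then with illustrative dropout of 10% versus 20% and 53 per arm, SE = √[(0.10 × 0.90 + 0.20 × 0.80)/53] = 0.0687 and z = 0.10/0.0687 = 1.46. Power is Φ(1.46 − 1.96) ≈ 0.31. Even a twofold difference would usually not set off the rule.

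**The case against.** A reader might infer that the SAP pools the arms without condition whenever missingness is similar. The text does not say so. It is silent on the default and lists no imputation variables, so condition is neither included nor excluded. Imputing the arms together does not in itself cause shrinkage either: condition must also be left out of the joint model.

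The conditional sentence stands in the paragraph on non-random missingness, whereas the check above uses random, equal dropout. MAR imputation is planned in the paragraph before, which has no by-condition rule at all. The 15% figure needs imputation from baseline alone, yet CPD is recorded daily and averaged weekly, so a sensible imputer would use more. The low power of the trigger also assumes a significance test that the SAP does not specify.

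All of this stands, and it limits the size and certainty of the point. It does not rescue the rule. The only stated reason for imputing by condition is one that does not determine whether condition is needed. Two statisticians following Section 7.6 could produce different robustness results, one of them attenuated.

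**Conclusion.** The trigger is wrong, and the SAP does not otherwise ensure that condition is in the imputation model. If missingness is similar in the arms and condition is omitted from a joint model, the multiple-imputation estimate shrinks. At 15% missing and a true difference of 5 CPD, the loss is about 15% (0.7 to 0.8 CPD) from baseline only, and roughly 1% to 13% when post-baseline CPD is used. The effect and the attrition are the documents' figures; the SD, correlations, dropout pattern and higher missing fractions are assumptions.

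Two stronger readings are not supported. The primary result is not biased by this rule, because it comes from maximum likelihood with condition in the model. Nor can the rule create a false effect, because the bias is toward no difference. The point concerns a sensitivity analysis and should be corrected before the data are analyzed.

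**What to change.** Delete the conditional clause in SAP 7.6. State that every multiple-imputation analysis, under both MAR and non-random missingness, respects condition in one of two ways:

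- separate imputation (PROC MI with BY condition); or
- a joint model that includes condition and lets its effect differ by visit.

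List the variables: baseline CPD and all 12 weekly CPD averages.

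The cost is a sentence or two and one line of code. Separate imputation fits each model of 13 CPD variables on about 53 women instead of 106. The joint model avoids that loss and, in the check above, removed the bias equally well.
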